9.3. Study Endpoints

9.3.1. Primary Endpoint for Phase 1

- Incidence of first cycle (28 days) DLTs to determine MTD and/or RP2D.

9.3.2. Secondary Endpoints for Phase 1

- ORR assessed by the Investigator using RECIST v1.1
- Pharmacokinetic parameters of repotrectinib
- Pharmacokinetic parameters of trametinib

9.3.3. Primary Endpoint for Phase 2

- ORR assessed by Investigator using RECIST v1.1.

9.3.4. Secondary Endpoints for Phase 2

- DOR, TTR, and CBR by the Investigator
- Intracranial objective response rate (IC-ORR) assessed according to modified RECIST v1.1 in subjects with brain metastases
- PFS and OS
- Type, incidence, severity, timing, seriousness, and relatedness (to each study drug) of AEs and laboratory abnormalities
- Pharmacokinetic parameters of repotrectinib

- Pharmacokinetic parameters of trametinib

9.3.5. Exploratory Endpoints for Phase 1b and Phase 2

- ORR and PFS by modulation of circulating tumor levels and genomic alterations observed pre- and post-dosing.

9.4. Statistical Analysis

9.4.1. General Considerations

Full descriptions of analyses to be performed will be included in the SAP and will supersede any analysis described here.

9.4.1.1. Missing Data

All analyses and descriptive summaries will be based on the observed data. Unless otherwise specified, missing data will not be imputed. Partial dates for AEs and concomitant medications will be imputed using the most conservative rules. Further details regarding missing data will be included in the SAP.

9.4.2. Efficacy Analyses

9.4.3. Analysis of Primary Endpoint

For Phase 1b, efficacy analysis will be performed in EE population. For Phase 2, the FAS analysis set will be used as the primary analysis for efficacy, and analyses using the EE population will be used as sensitivity analysis. Primary efficacy data will be based on the radiologic assessments evaluated by the Investigator. Data from BICR may be analyzed as supportive.

For Phase 2, the primary efficacy endpoint is ORR of repotrectinib in combination with trametinib in subjects with advanced/metastatic solid tumors harboring *KRAS* mutations potential biomarkers, including genomic alterations that could predict efficacy or resistance to the study drugs, may be explored.

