3.2.1.1. Dose-Limiting Toxicities

Subjects are eligible for DLT evaluation if they experience a DLT during the first cycle of treatment (i.e., 28 days) or do not experience a DLT during the first cycle of treatment while able to receive at least 75% of planned doses during the first cycle of treatment. Subjects who do not fulfill these requirements will be replaced for DLT evaluation but will remain in the overall safety and efficacy analyses.

A DLT is defined as an AE or abnormal laboratory value assessed as unrelated to disease progression, intercurrent illness, or concomitant medications that meets any of the criteria in [Table 3](#).

Table 3: CTCAE Dose-Limiting Toxicities

Category ^a	Criteria
Toxicities resulting in an excessive number of missed doses	
 Inability to deliver at least 75% of the planned doses of repotrectinib and trametinib during Cycle 1 treatment because of toxicity attributed to study drug (excluding toxicities clearly related to disease progression or intercurrent illness)
Hematologic toxicities	
 Grade \geq 4 neutropenia ($\text{ANC} < 500/\text{mm}^3$) lasting > 7 days Grade \geq 4 platelet count decrease (platelets $< 25,000/\text{mm}^3$) or Grade ≥ 2 ($< 75,000/\text{mm}^3$) associated with clinically significant bleeding Grade \geq 4 anemia Grade \geq 3 febrile neutropenia (defined as $\text{ANC} < 1,000/\text{mm}^3$ with a single temperature of $\geq 38.3^\circ\text{C}$ [$\geq 101^\circ\text{F}$] or a sustained temperature of $\geq 38^\circ\text{C}$ [$\geq 100.4^\circ\text{F}$] for > 1 hour)
Renal	
 Grade \geq 3 creatinine increase ($> 3 \times$ upper limit of normal [ULN])
Hepatic	
 Grade \geq 3 total bilirubin elevation ($> 3 \times$ ULN) Grade \geq 2 total bilirubin elevation ($> 1.5 \times$ ULN) and grade ≥ 2 ALT or AST elevation ($> 3 \times$ ULN) Grade 3 ALT elevation ($> 5 \times$ ULN) that does not resolve to grade ≤ 1 within 7 days or any grade ≥ 4 ALT elevation Grade 3 AST elevation ($> 5 \times$ ULN) that does not resolve to grade ≤ 1 within 7 days or any grade ≥ 4 AST elevation Grade 4 elevations in ALP
Pancreatic	
 Grade \geq 3 amylase or lipase elevation
Cardiac	
 Grade \geq 3

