9.1.2. Efficacy Evaluable Analysis Set

Efficacy Evaluable (EE) Analysis Set will include all enrolled subjects who (1) have received at least one dose of study treatment with repotrectinib; (2) *KRAS* mutation determined by a qPCR or NGS test performed in a CLIA laboratory or equivalently accredited diagnostic laboratory; (3) have a baseline tumor assessment with measurable disease and have at least 1 on-study tumor assessment per RECIST v1.1; and (4) have no major protocol violations that could affect efficacy.

The EE Analysis Set will be used for efficacy analyses for Phase 1b, and sensitivity analysis of efficacy endpoints for Phase 2.

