9.4.3.1. Objective Response Rate

The ORR will be defined as the proportion of subjects with a confirmed CR or PR. A confirmed response is a response that persists on a repeat imaging performed at least 4 weeks after initial documentation of response. Subjects with a confirmed objective response (CR or PR) will be referred to as responders. Non-responders will include subjects without a confirmed objective response, SD, progressive disease (PD), not evaluable (NE), or non-CR/non-PD (NN). The ORR will be reported as the proportion of responders by RECIST v1.1 along with the corresponding two-sided 95% Clopper-Pearson exact CI.

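### Phase 1b ORR is analysed only in the Efficacy Evaluable set, so treated subjects who are never scanned on study leave the denominator, and no all-treated analysis is named beside it.

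*Combined protocol and SAP*

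**What the plan says.** Two sections assign the analysis set. Section 9.4.3: "For Phase 1b, efficacy analysis will be performed in EE population". Section 9.1.2: "The EE Analysis Set will be used for efficacy analyses for Phase 1b, and sensitivity analysis of efficacy endpoints for Phase 2". Phase 2 is handled the other way round in Section 9.4.3: "For Phase 2, the FAS analysis set will be used as the primary analysis for efficacy".

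To enter the Efficacy Evaluable (EE) set a subject must, among other conditions, "have a baseline tumor assessment with measurable disease and have at least 1 on-study tumor assessment per RECIST v1.1" and "have no major protocol violations that could affect efficacy". No exception is written for death, clinical progression or toxicity before the first scan.

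Two other places bear on who should be counted:

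- Section 3.2.1.1, and the matching synopsis text on dose-limiting toxicities (DLTs), says that subjects replaced for DLT evaluation "will remain in the overall safety and efficacy analyses".
- Section 9.4.3.1 defines the non-responder class: "Non-responders will include subjects without a confirmed objective response". Not-evaluable subjects are in that class.

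Section 9.3.2 lists investigator-assessed ORR as a secondary endpoint of Phase 1.

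**The concern.** Whether a subject has an on-study scan is known only after treatment starts, and it depends on how the subject fares. Those most likely to have none are those who deteriorate or die early, and none of them can have a confirmed response. Removing them takes failures out of the denominator and nothing out of the numerator.

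The non-responder rule in Section 9.4.3.1 does not repair this. It classifies subjects who are already in the analysis set and cannot bring back those whom Section 9.1.2 has excluded. Section 9.4.1.1 works from observed data without imputation, so it does not bring them back either. For Phase 2 the plan avoids the problem by using the FAS as the main set. For Phase 1b it names no all-treated efficacy analysis, even as a sensitivity analysis.

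At stake is the reading of Phase 1b activity by dose level. Section 3.2 lists preliminary efficacy within each dose level among the data for escalation decisions, and Section 3.2.1.3 lists efficacy among the inputs to the RP2D.

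**Working it through.** **The plan's own figure.** The only ORR estimate in the plan is the Phase 2 one in Section 9.2.1.2: 21 of 56, given as 38% (95% CI 25 to 51). By the two-sided Clopper-Pearson method of Section 9.4.3.1, 21/56 = 37.5% with limits 24.9% and 51.5% (51.45 before rounding). That reproduces the stated figure. No ORR is stated for Phase 1b.

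**Who is lost.** The first scheduled on-study scan is at Cycle 3 Day 1, after two 28-day cycles (Table 1, footnote 19). Two rules produce scans in subjects who stop treatment early:

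1. Section 6.16 requires an end-of-treatment (EOT) scan if more than 4 weeks have passed since the last imaging and treatment stops for a reason other than confirmed radiographic progression.
2. Sections 3.4, 6.16 and 7.4 continue tumor assessments after treatment stops without radiographic progression, until progression, new anticancer therapy or a decision to stop treating. Footnote 19 and Section 6.16 add withdrawal of consent as an end point.

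Reading scans under both rules as on-study assessments (Section 9.1.2 does not say), the subjects lost are those who die, withdraw, start new therapy or move to supportive care with no scan at all.

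**Direction.** Let n be treated subjects, x confirmed responders and d treated subjects with no on-study scan. A confirmed response needs a repeat scan at least 4 weeks after the first, so no unscanned subject is counted in x.

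- All-treated ORR = x/n
- ORR after the scan criterion = x/(n - d)
- Ratio = n/(n - d) = 1/(1 - f), with f = d/n

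For x of at least 1, the ratio is 1 when d = 0 and above 1 otherwise. With x = 0 both rates are zero.

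**Size.** The documents give no f, so the range is an assumption: f = 0 gives 1.00; f = 10% gives 1/0.90 = 1.11; f = 20% gives 1/0.80 = 1.25; f = 33% (one third) gives 1.50.

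Section 9.2.1.1 plans 3 to 6 DLT-evaluable subjects per dose level and about 24 to 30 in total. The values of x and d below are illustrations.

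| Treated | Responders | Unscanned | All-treated ORR (95% CI) | ORR after scan criterion (95% CI) |
|---|---|---|---|---|
| 6 | 1 | 1 | 16.7% (0.4 to 64.1) | 1/5 = 20.0% (0.5 to 71.6) |
| 6 | 1 | 2 | 16.7% (0.4 to 64.1) | 1/4 = 25.0% (0.6 to 80.6) |
| 6 | 2 | 1 | 33.3% (4.3 to 77.7) | 2/5 = 40.0% (5.3 to 85.3) |
| 30 | 6 | 2 | 20.0% (7.7 to 38.6) | 6/28 = 21.4% (8.3 to 41.0) |
| 30 | 6 | 6 | 20.0% (7.7 to 38.6) | 6/24 = 25.0% (9.8 to 46.7) |

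**The two rules side by side.** Section 3.2.1.1 keeps replaced subjects in the efficacy analyses. Section 9.1.2 removes any of them who has no scan. For a subject who is both replaced and unscanned, both statements cannot hold.

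**Pooling.** Section 9.2.1.2 pools up to 6 Phase 1b subjects treated at the RP2D with 50 Phase 2 subjects and works with 50 + 6 = 56. It does not name the analysis set for those 6.

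**The case against.** The strongest reply is that few subjects would be lost. The EOT scan and the continued off-treatment scans keep many early stoppers in the EE set, including a subject who stops for toxicity and is then scanned. This stands, and it rules out the reading that everyone who fails before Cycle 3 Day 1 disappears. It does not close the gap. The EOT scan is not required within 4 weeks of the last imaging, and continued scanning ends at new therapy or supportive care.

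Second, the whole EE set need not flatter the drug. Its exclusion for major protocol violations could remove responders, so the EE rate could fall below the all-treated rate. This also stands. The one-way direction belongs to the scan criterion alone.

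Third, a reader might infer that the inflated rate drives the dose choice. The documents do not support that. Section 3.2.1.3 rests the RP2D on all the safety, efficacy and pharmacology data. Its efficacy clause asks whether responses or prolonged stable disease occur below the maximum tolerated dose, which the denominator cannot change. With 3 to 6 subjects per level, the intervals are far wider than the shift.

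Fourth, Section 3.2.1.1 can be read as saying only that failing DLT evaluability is not itself a reason for removal. That narrows the conflict to replaced subjects with no scan but does not remove it.

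Last, Sections 9 and 9.4.1 let a later SAP modify or supersede this text. It may, but the documents as they stand contain no correction.

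**Conclusion.** The point holds for Phase 1b ORR as a secondary, descriptive endpoint. As written, treated subjects with no on-study scan leave the denominator, and the scan criterion raises ORR by 1/(1 - f) or leaves it unchanged. Under the assumed f of 0 to 33% the factor is 1.00 to 1.50. The true f cannot be derived from the documents, and if every treated subject is scanned there is no effect. The consequence for the RP2D is limited.

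A reader might also infer that the pooled Phase 1b subjects enter the Phase 2 primary analysis on the EE set while the others enter on the FAS. The text does not say so: the set is unstated, and the denominator of 56 is the full 50 + 6. The silence is still worth closing. If the EE set were applied to them and 3 were unscanned, 19 responders would give a lower 95% limit of 23.1% (19/53) instead of 21.8% (19/56), on either side of the 23% criterion. That is an edge case that depends on a reading the plan does not state.

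This is a cheap improvement that is worth making; it does not put the primary endpoint in doubt.

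**What to change.** - In Sections 9.1.2 and 9.4.3, make all treated subjects (the FAS) the main set for Phase 1b ORR, by dose level and overall, and count subjects with no on-study scan as non-responders.
- Keep the EE set as a sensitivity analysis, as in Phase 2, and report how many subjects it excludes and why.
- In Section 9.2.1.2, state that the Phase 1b subjects pooled at the RP2D are analysed on the FAS.
- Reconcile Section 3.2.1.1 and the matching synopsis text with Section 9.1.2, so that the treatment of a replaced subject with no scan is stated once and consistently.

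This takes a few sentences and needs no new data, visits or subjects. The one cost is that the Phase 1b ORR may be slightly less favourable.

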9.4.3.1. Objective Response Rate

The ORR will be defined as the proportion of subjects with a confirmed CR or PR. A confirmed response is a response that persists on a repeat imaging performed at least 4 weeks after initial documentation of response. Subjects with a confirmed objective response (CR or PR) will be referred to as responders. Non-responders will include subjects without a confirmed objective response, SD, progressive disease (PD), not evaluable (NE), or non-CR/non-PD (NN). The ORR will be reported as the proportion of responders by RECIST v1.1 along with the corresponding two-sided 95% Clopper-Pearson exact CI.

9.4.4. Analysis of Secondary Endpoints

The secondary efficacy endpoints include DOR, TTR, CBR, intracranial response, PFS, and OS of repotrectinib in combination with trametinib in subjects with advanced or metastatic solid tumors harboring *KRAS* mutations. Potential biomarkers, including genomic alterations that

could predict efficacy or resistance to the study drugs, may be explored. Further details regarding these secondary efficacy analyses will be included in the SAP.

9.4.5. Safety Analyses

Safety analyses will be performed using the Safety Analysis Set for each cohort, as well as for all cohorts combined. Further descriptions of the analyses of safety endpoints including adverse events coded to Medical Dictionary for Regulatory Affairs (MedDRA) version 23.0 or higher, deaths, laboratory results, ECG results, vital signs, and left ventricular ejection fraction (LVEF) will be described in the SAP.

9.4.6. Analysis of Pharmacokinetics

9.4.6.1. Single-and Multiple-Dose Repotrectinib and Trametinib Pharmacokinetic Analysis

Repotrectinib and trametinib plasma concentration-time data will be analyzed using non-compartmental methods to estimate the following PK parameters in individual subjects: maximum plasma concentration (C_{max}), time to maximum plasma concentration (T_{max}), area under the plasma concentration-time curve (AUC). If data permit or if considered appropriate, area under the plasma concentration versus time curve to infinity (AUC_{inf}), terminal elimination half-life ($t^{1/2}$), apparent plasma clearance (CL/F), apparent volume of distribution (Vz/F), and accumulation ratio (R_{acc}) will be estimated. The single- and multiple-dose PK parameters will be summarized descriptively by dose, cycle, and day.

Repotrectinib and trametinib concentrations will be summarized descriptively (n, mean, standard deviation, CV, median, minimum, maximum, geometric mean and its associated CV) by dose, cycle, day and nominal time. Individual, mean, and median profiles of the concentration-time data will be plotted by dose, cycle and day (single-dose, and multiple-dose) using nominal time. Median and mean profiles will be presented on both linear and log-linear scales.

Dose normalized AUC_{inf} , (AUC_{τ} at steady state), AUC_{last} , and C_{max} will be plotted against dose (using a logarithmic scale) by cycle and day. These plots will include individual subject values and the geometric means for each dose. These plots will be used to help understand the relationship between PK exposure and dose.

The observed R_{acc} will be summarized descriptively. It will be analyzed after natural log transformation using a one-way analysis of variance with a single term for dose. The means and 90% confidence intervals (CIs) obtained from the model will be back-transformed to provide means and 90% CIs for the accumulation and linearity ratios for each dose.

Trough concentrations will be plotted for each dose using a box-whisker plot by cycle and day within cycle to assess the attainment of steady state.

9.5. Interim Analysis

Periodic reviews of the preliminary data may be performed for executive, regulatory, and/or conference presentation purposes.

In addition, for Phase 2, an interim futility analysis of the ORR will be performed after approximately 15 subjects are evaluable for tumor response to safeguard future patients from

exposure to a potentially ineffective treatment. Depending on the enrollment rate, it is anticipated that approximately 20-30 subjects will be enrolled at the interim analysis.

The interim futility stopping rule for the maximum number of responders (R) required among the 15 (N) evaluable subjects with the cumulative probability of observing $\leq R$ responders under the targeted ORR (P1) and futility ORR (P0) is shown in [Table 10](#). If ≤ 2 responders (confirmed CR or PR) are observed from 15 evaluable subjects, the expansion cohort will be stopped for futility. If ≥ 3 responders are observed, this cohort may continue depending on the overall benefit and risk assessment at the interim analysis. If the true ORR in this cohort is as targeted at 38%, the probability of observing ≤ 2 responders is 3.8%. If the true ORR is significantly lower than the target ORR (i.e., 10% instead of 38%), the probability is 81.6%.

Table 10: Stopping Rule for Interim Futility Analysis of ORR in Phase 2

N	R	Target ORR (P1)	Futility ORR (P0)	Probability Under P1	Probability Under P0
15	2	38%	10%	0.038	0.816

Abbreviations: EXP = expansion; ORR = overall response rate; P1 = target overall response rate; P0 = futility overall response rate.

Note: N is the number of evaluable patients for tumor response at the interim futility analysis and R is the maximum number of responders (confirmed CR or PR) for futility stop. If the number of responders is $\leq R$, the cohort will be stopped for futility.

10. QUALITY CONTROL AND QUALITY ASSURANCE

It is the Investigator's responsibility to ensure the accuracy, completeness, and timeliness of the data reported for each subject. Source documentation supporting the data should indicate the subject's participation in the study and should document the dates and details of study procedures, AEs, and subject status.

To ensure compliance with GCP and all applicable regulatory requirements, the Sponsor may conduct a quality assurance audit.

11. DATA HANDLING AND RECORD KEEPING

11.1. Case Report Forms/Electronic Data Record

After data have been entered into the study database, a system of computerized data validation checks will be implemented and applied to the database on a regular basis. Queries will be entered, tracked, and resolved directly through the electronic data capture (EDC) system. The study database will be updated in accordance with the resolved queries. All changes to the study database will be documented.

11.2. Study Monitoring, Audits, and Inspections

Site visits will be conducted by an authorized Sponsor representative, who will inspect study data, subjects' medical records, and CRFs according to GCP, the Food and Drug Administration (FDA), and the International Conference on Harmonisation (ICH) guidelines. In addition to monitoring by the Sponsor or its designees, the study may be audited by representatives of the FDA or other regulatory authorities, who will also be permitted access to study documents. The

Investigator should immediately notify the Sponsors' Clinical Operations department or designee of any proposed or scheduled audits by regulatory authorities.

The Investigator will permit authorized representatives of the Sponsor or designee and national or local health authorities to inspect facilities and records relevant to this study.

The Investigator must obtain Institutional Review Board (IRB)/EC approval for the investigation. Initial IRB/IEC approval and all materials approved by the IRB/EC for this study, including the subject consent form and recruitment materials, must be maintained by the Investigator and made available for inspection.

11.3. Inspection of Records

The Sponsor and designees of the Sponsor will be allowed to conduct site visits to the investigational facilities for monitoring any aspect of the study. The Investigator agrees to allow Sponsor representatives to inspect the drug storage area, investigational product inventory, drug accountability records, subject charts and study source documents, and other records relative to the study conduct.

11.4. Record Retention

The Investigator will coordinate with the study site to ensure all documentations relating to the study for a period of 2 years after marketing application approval or, if not approved, 2 years after the notification to the FDA of the discontinuance of the investigational product for investigation. If it becomes necessary for the Sponsor or the Regulatory Authority to review any documentation relating to the study, the Investigator must permit access to such records.

The records should be retained by the Investigator according to ICH, local regulations, or as specified in the Clinical Trial Agreement, whichever is longer; but at a minimum, all study documentation must be retained for 2 years after the last marketing application approval in an ICH region or after at least 2 years have elapsed since formal discontinuation of clinical development of repotrectinib.

12. ETHICS

12.1. Ethics Review

The final study protocol, including the final version of the ICF, must be approved or given a favorable opinion in writing by an IRB/IEC, as appropriate. The Investigator must submit written approval to the Sponsor before he or she can present informed consent and begin screening activities for any subject in the study.

The Investigator is responsible for informing the IRB/IEC of any amendment(s) to the protocol in accordance with local requirements. In addition, the IRB/IEC must approve all advertising used to recruit subjects for the study, if applicable. The protocol must be re approved by the IRB/IEC upon receipt of amendments and annually, as local regulations require.

The Investigator is also responsible for providing the IRB/IEC with reports of any reportable serious adverse drug reactions from any other study conducted with the investigational product. The Sponsor will provide this information to the Investigator.

Progress reports and notifications of serious adverse drug reactions will be provided to the IRB/IEC according to local regulations and guidelines.

